7 STUDY INTERVENTION DISCONTINUATION AND SUBJECT DISCONTINUATION/WITHDRAWAL

7.1 DISCONTINUATION OF STUDY INTERVENTION

For Subjects Who Develop an Infection:

Subjects who, during the course of the Treatment Phase, develop clinical signs and/or symptoms of infection (e.g., erythema, edema, pain, inflammation, increased drainage etc.) and in the opinion of the Investigator, require oral antibiotic therapy may receive a single course of oral antibiotics during the Treatment Phase of the study. **Should a second consecutive course be required/desired, the subject will be exited from the study.** This antibiotic therapy will be noted on the Concomitant Medications eCRF.

In addition to the above, for those subjects receiving Apligraf or AMNIOEXCEL Plus and develop signs/symptoms of infection, application of those allografts will be withheld on that visit. Application of allografts may be withheld for no more than 1 week at a time and no more than twice (non-consecutive visits) during the 12-week Treatment Phase. If signs and symptoms of infection requiring antibiotic therapy persist for more than one visit, or appear on more than 2 non-consecutive visits during the Treatment Phase, the subject will be discontinued from study participation.

For Subjects Whose Wound Closes:

Discontinuation from treatment in any of the study cohorts does not mean discontinuation from the study. There is one scenario in which a subject may continue in the study after intervention is final:

After treatment with AMNIOEXCEL Plus, Apligraf, and/or SOC **AND** if the subject's wound is documented as closed at or before week 12, the subject will continue to be monitored for two weeks to confirm wound closure. This is noted as week 13 and 14 in the Schedule of Activities, above, but may occur earlier.

If the subject's wound has NOT closed by week 12, the subject will be considered a study failure and will not have any further study visits.

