8.1.5 WEEK 12 (84 ± 3 DAYS)

1. Review Study Compliance with the Subject (Treatment Compliance Review)
2. Collect MRU Data for the Previous Week (MRU Assessment)
3. Collect Images of the DFU (Photography)
4. Perform Ulcer Assessments
5. Apply Boot, if applicable
6. Document Adverse Events
7. Document Concomitant Medications & Procedures (ConMeds and Other Procedures)

8.1.6 FOLLOW-UP VISITS - WEEKS 13 & 14 (91 & 98 ± 3 DAYS)

1. Collect MRU Data for the Previous Week (MRU Assessment)
2. Collect Images of the DFU (Photography)
3. Perform Ulcer Assessments
4. Apply Boot, if applicable
5. Document Adverse Events

6. Document Concomitant Medications & Procedures (ConMeds and Other Procedures)

IMPORTANT: If the subject’s wound is open at Follow-up visit 1 (e.g., week 13), the subject is exited from the study and is marked as having completed their study requirements. The site will note why they believe the wound is still open.

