8.3.7 TIME PERIOD AND FREQUENCY FOR EVENT ASSESSMENT AND FOLLOW-UP

The occurrence of an adverse event (AE) or serious adverse event (SAE) may come to the attention of study personnel during study visits and interviews of a study subject presenting for medical care, or upon review by a study monitor. All AEs will be captured on the appropriate eCRF as noted above in section 8.2.

Any medical condition that is present at the time that the subject is initially screened will be considered as pre-existing and not reported as an AE. However, if the study subject’s condition deteriorates at any time during the study, it will be recorded as an AE.

Changes in the severity of an AE will be documented to allow an assessment of the duration of the event at each level of severity to be performed. AEs characterized as intermittent require documentation of onset and duration of each episode.

The study Investigator will record all reportable events with start dates occurring any time after informed consent is obtained the last day of study participation (i.e., Follow-Up Visit 2). At each study visit, the investigator will inquire about the occurrence of AE/SAEs since the last visit. Events will be followed for outcome information until resolution or stabilization.

If an AE is not resolved by the end of the study, that event will be marked as such by the Investigator.

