8.3.9 SERIOUS ADVERSE EVENT REPORTING

Investigators are instructed to report SAEs to Integra within 10 business days of the Investigator becoming aware of the SAE.

SAEs must be reported by the Investigator to Integra by completing the SAE eCRF. All SAEs and deaths that are possibly related, probably related, or definitely related to the investigational product or study procedures must be reported. The information collected will include a minimum of the following: subject number, a narrative description of the event, lot number of device used on subject, and an assessment by the Investigator as to the intensity of the event and relatedness to study device. Follow-up information on the SAE may be requested by the Sponsor.

Any subjects reporting SAEs that have not resolved by their last treatment visit will be followed via phone or clinic visit through resolution or 14 days post final visit, whichever comes first.

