9.4.7 SAFETY ANALYSES

AEs/SAEs related to the investigational product, study ulcer and/or study procedures and will be recorded.

AEs will be coded according to the most recent version of the Medical Dictionary for Regulatory Activities (MedDRA) AE coding dictionary, and grouped by body system. The number and percentage of subjects experiencing at least one AE of any type, AEs within each body system and AEs within each preferred term will be presented for each treatment group. Separate summaries will be provided for all AEs, device related AEs, SAEs and AEs leading to withdrawal.

All safety parameters will be summarized descriptively by treatment assignment. No inferential statistics are planned.

Listings of complications will be presented, include complication type, relation to study device, relation to procedure, action taken, and clinical outcome. Separate listings will be constructed for complications with possible, probable, or definite relationship to the device, serious complications, and for all complications. The listing for all complications will be sorted by complication type.

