10.6. Safety Analysis

Safety will be assessed through reports of adverse events and serious adverse events. Adverse Events related to the device, study ulcer and/or study procedures and all Serious Adverse Events will be recorded.

All safety parameters will be summarized descriptively by treatment. No inferential statistics are planned.

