10.7. Adverse Events

Adverse events will be coded using the MedDRA Medical Dictionary. Treatment Emergent AE's (TEAE) are defined as events with an onset on or after the first randomized treatment. TEAEs will be summarized by treatment group, System Organ Class, and preferred term. The following TEAE summaries will be provided:

- TEAEs by severity grade
- TEAEs by relationship to study treatment.

In addition, separate summaries of serious adverse events, and adverse events resulting in discontinuation of study treatment will be presented.

The safety population will be used for the safety analyses. Summary will be provided by subject and by adverse events. Subjects will be counted only once for subject-based analysis.

Confidential Page 18 of 23

If the same event changes in severity for a subject, the worst severity will be reported. Subjects could be counted more than once for AE-based analysis, all AEs will be reported for AE-based analysis.

An adverse event is considered to be treatment emergent if (1) it was not present when the active phase of the study began, and it is not a chronic condition that is part of the subject's medical history; or (2) it is present at the start of the study or as part of the subject's medical history, but the severity or frequency increased during the active phase. The active phase of the study begins on the day of the first dose of test article and the last dose of test article.

Treatment-emergent adverse events (TEAE) will be summarized for each treatment group by body system and preferred term. The severity of all adverse events will be determined by the investigator's judgment and classified as mild, moderate or severe.

Treatment groups will be compared with respect to the incidence of adverse events (all and TEAEs) and the proportion of subjects withdrawing from the study for adverse events by reason of withdrawal. Comparisons will be made overall, by body system and by preferred term and will be further categorized by severity and by study drug relationship.

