11.1.3. Other Variables

Discontinuations

The difference between treatments, both overall and for each primary reason, will be compared by using a 2-sided Fisher's exact test.

Confidential Page 22 of 23

Demographic and Baseline Characteristics

Comparisons between treatment groups of continuous variables will be made by using a one-way analysis of variance with treatment as a factor. For categorical variables, the Fisher's exact test will be used. All tests will be 2-sided and performed at the 0.05 level of significance.

Time-to-Event Data

Time-to-event endpoints including time-to-complete-wound-closure/healed will be evaluated using the Kaplan-Meier method. The log-rank test will be used to compare the distributions between two treatment groups.

Rate of Wound Closure, as Assessed by Computerized planimetry

Analysis of Covariance (ANCOVA) will be used to compare the rate of wound closure for the two treatment groups.

Safety Data

The primary safety endpoint for this study is any severe device-related complication where relationship to the device was assessed by the clinical event committee possible, probably, or definite. Fisher's exact test will be used to compare incidence rates of serious device-related complications as well as for any device-related complication, and for specific complications between the treatment group and the control group.

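### Adverse-event observation time depends on when and whether the wound closes, but the SAP compares crude incidence between arms with no account of exposure

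*SAP*

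**What the plan says.** **Collection window.** Protocol 8.3.1 collects events that start or worsen after the first randomized treatment, through study exit. Protocol 8.3.7 puts the end at "the last day of study participation (i.e., Follow-Up Visit 2"), a visit that only subjects still closed at the first follow-up visit have (Schedule of Activities, footnote b).

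**Exit.**
- Closed: followed for two weeks after closure (Protocol Table 1, Subject Duration; Protocol 7.1, which notes that the visits labelled Weeks 13 and 14 may occur earlier).
- Open at Week 12: the subject "will be considered a study failure and will not have any further study visits" (Protocol 7.1).
- Open at Follow-up Visit 1: "the subject is exited from the study and is marked as having completed their study requirements" (Protocol 8.1.6).
- Infection rules, withdrawal or discontinuation: observation ends at that exit (Protocol 7.1 and 7.2).

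After exit, only unresolved SAEs are pursued, "followed via phone or clinic visit through resolution or 14 days post final visit, whichever comes first" (Protocol 8.3.9).

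**Analysis.** Protocol 9.4.7 tabulates "The number and percentage of subjects experiencing at least one AE of any type". SAP 10.7 adds event counts and compares arms on incidence: "Treatment groups will be compared with respect to the incidence of adverse events (all and TEAEs"). SAP 11.1.3 adds a test: "Fisher's exact test will be used to compare incidence rates of serious device-related complications", and extends it to any device-related complication and to specific complications. SAP 10.6 says the opposite: "All safety parameters will be summarized descriptively by treatment. No inferential statistics are planned". SAP Equation 2 computes each subject's duration in the trial, but no adverse-event analysis uses it.

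**The concern.** The chance of recording at least one event grows with the weeks observed, and here those weeks are partly a result of treatment. A wound that closes at Week 2 is watched for about 4 weeks; one that never closes is watched for 12. When arms differ in how quickly wounds close, the percentage of subjects with an event mixes time under observation with risk per unit time. This trial is set up to compare closure and time to closure, so such a difference is a realistic outcome. The three-arm safety comparison could then show a gap that reflects length of follow-up, and the documents plan no table that would let a reader see this.

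**Working it through.** **Plan's own figure.** The plan gives no adverse-event rate or closure-time curve, so there is no safety figure to reproduce. Its one computed design figure, the 13.5% half-width, concerns closure. It reproduces as a between-arm difference, 1.96 × √(2 × 0.9 × 0.1 / 38) = 13.49%, and does not bear on this point.

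**Observation time, from the exit rules.** Closure at week k gives k + 2 weeks; never closed gives 12 weeks. Break-even is k + 2 = 12, so k = 10. Closure at Week 11 or 12 gives 13 or 14 weeks, longer than a wound that stays open.

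**Simple illustration.** Assumed, not in the documents: the same constant hazard of 3% per week in both arms. P(event) = 1 − exp(−0.03 × weeks), which is 0.2134 at 8 weeks, 0.2592 at 10 and 0.3023 at 12.
- Arm X, 80% close at Week 6 (8 weeks), 20% stay open: mean 0.8 × 8 + 0.2 × 12 = 8.8 weeks. Incidence 0.8 × 0.2134 + 0.2 × 0.3023 = 23.1%.
- Arm Y, 40% close at Week 8 (10 weeks), 60% stay open: mean 0.4 × 10 + 0.6 × 12 = 11.2 weeks. Incidence 0.4 × 0.2592 + 0.6 × 0.3023 = 28.5%.

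The gap is 5.4 points with no difference in weekly risk.

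**Range.** A second model uses a constant weekly chance of closure, set to give the stated closure by Week 12, and a weekly risk h of a first event that is equal in both arms. Incidence is the sum over exit weeks of P(exit week) × [1 − (1 − h)^weeks].

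| Closure by Week 12 | Mean weeks | Incidence, h = 3% | Incidence, h = 5% |
|---|---|---|---|
| 90% | 6.95 | 18.7% | 29.0% |
| 70% | 8.73 | 22.9% | 35.0% |
| 50% | 9.91 | 25.7% | 39.0% |
| 30% | 10.84 | 27.9% | 42.1% |

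Over h from 1% to 8% and the unequal closure pairs tried, the ratio of crude incidences (faster over slower arm) runs from 0.65 to 0.93. With equal closure curves it is 1.

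**Reversal.** If closures fall only in Weeks 11 and 12, split evenly, then at h = 5% an arm with 90% closure shows 49.6% and one with 30% closure shows 47.2%.

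**Early exits.** At h = 5%, adding 20% early exits to the arm with 50% closure lowers its incidence from 39.0% to 36.1%, still above the 29.0% at 90% closure.

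**Fisher's exact test.** Applied at 38 per arm to an event with h = 5%, it favours the faster arm in 10.3% of trials (90% vs 50% closure), against 1.4% in that direction when closure is equal. Device-related complications, the outcome the SAP names for this test, may be rarer than the assumed 5% per week.

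**TEAE window.** SAP 10.7 also bounds the active phase by the last dose. Counting k − 1 weeks for closure at week k, and 11 if never closed, the h = 5% figures for 90% vs 50% closure become 17.8% vs 31.9%.

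**Check of the remedy.** First events divided by subject-weeks at risk return the common risk in both arms (0.030 and 0.030; 0.050 and 0.050, at 90% and 30% closure).

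**The case against.** A reader might infer that the faster-healing arm will always look safer. The documents do not support that. Closures at Weeks 11 and 12 are observed longer than open wounds, early exits can offset the effect, and the plan's own sample-size assumption is no difference in closure between cohorts. The artefact is zero if that equality extends to the whole closure curve. That assumption sets precision, however; it does not remove the need for readable safety tables if the arms do differ.

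The size is also modest against the noise: 5.4 points is about 2 of 38 subjects, and the 95% interval for that difference is about ±20 points. This stands, and both documents say the study is inadequate for hypothesis testing.

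Equal weekly risk may not hold. Product and dressings stop at closure, so fewer wound-related events after early closure could be a real benefit. This stands too, and the illustrations are conditional on equal risk.

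Rates alone can mislead in the other direction. If 10% of each arm reacts in Week 1 and nothing happens later, crude incidence is equal, but the exposures above give 10/8.8 = 1.14 and 10/11.2 = 0.89 per 100 subject-weeks, a 27% excess in the faster arm. Rates therefore belong beside the percentages, not in their place.

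A reader might also take the different wording of Protocol 8.3.7 and 8.3.9 on how long events are followed as part of this bias. It concerns events already recorded and cannot change incidence. Likewise, study exit in Protocol 8.3.1 already covers every route; the mention of Follow-Up Visit 2 in 8.3.7 is loose wording.

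**Conclusion.** The concern holds in a conditional form. Observation time depends on closure, and neither document adjusts for it in any safety comparison. If closure speed differs between arms, crude incidence can differ at equal weekly risk, with a direction that depends on whether closures come before or after Week 10. The illustrated size is 23.1% vs 28.5% at an assumed 3% per week, with crude ratios of 0.65 to 0.93 across the constant-closure scenarios tried. These figures rest on assumed event rates, closure patterns and constant equal weekly risk. The primary efficacy analysis is unaffected. SAP 10.6 does not dispose of the point: SAP 10.7 and 11.1.3 plan comparisons and tests, and crude percentages can mislead even when only described.

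**What to change.** In SAP 10.7:
- Tabulate subject-weeks of observation by arm, from first treatment to actual exit. Define exit for every route. Equation 2a uses a final follow-up visit date, which subjects open at Week 12 do not have.
- Report AEs, SAEs and wound-related AEs per 100 subject-weeks, or time to first AE, beside the crude percentages.
- Match the denominator to the TEAE window in use. A window ending at the last dose needs time to the last dose, not time to exit.
- Read any between-arm safety statement with both measures in view, not from crude incidence alone.

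Reconcile SAP 10.6 with SAP 10.7 and 11.1.3 on whether safety inference is planned.

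As a separate clarification, reconcile Protocol 8.3.7 with 8.3.1 on the end of recording, and with 8.3.9 on the end of follow-up.

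The cost is a few table columns and some wording. Visit, withdrawal and event-onset dates are already collected, and no visit or treatment changes. The drawback is that rates assume a roughly constant hazard, which is why the crude percentages stay.

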Primary Endpoint:	The primary endpoint of this study is the incidence of complete wound closure, as assessed by the Investigator at or before Week 12 of the Treatment Phase, which is confirmed closed two weeks later. Complete wound closure is defined as complete skin re-epithelialization that is without drainage or dressing requirements
Secondary Endpoint(s):	1. The proportion of subjects in each group with complete closure of the study ulcer at or before Week 12 as assessed by computerized planimetry.

	
 2. The proportion of subjects in each group with complete wound closure of the study ulcer at or before Week 12 as assessed by independent, blinded, assessment of photographs. 3. The time to complete wound closure, as assessed by the Investigator. 4. The time to complete wound closure for all closed wounds in each group, as assessed by computerized planimetry. 5. For those wounds that have closed, the rate of wound closure for each group, as assessed by computerized planimetry. 6. Medical resource utilization associated with management of DFU and related complications as determined by a comparison of estimated costs from the presumed billing codes which would have been used for each patient.

Safety Endpoint:
	
Incidence of all investigational product, procedure, and/or wound-related adverse events or serious adverse events.

Exploratory Endpoint(s):
	
 1. The proportion of closed wounds in each group at Week 4 of the Treatment Phase 2. Co-variate analyses of the primary endpoint using those listed in section 9.3.

Description of Study Intervention(s):
	
Intervention 1: SOC therapy consisting of the use of moist wound dressings, debridement, infection surveillance and management and consistent and appropriate use of an offloading boot.
 
Intervention 2: AMNIOEXCEL Plus used in conjunction with SOC therapy.
 
Intervention 3: Apligraf used in conjunction with SOC therapy.

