- Deteriorating ulceration (non-study site)
- Gastroenteritis
- Cataract
- Abscess (overall body)
- Gastritis
- Spontaneous bone fracture
- Diarrhea
- Positive Wound Culture (study site)
- Arthrosis (non-study site)
- Malaise
- Rash (study site)
- Hematoma (study site)
- Gangrene (non-study site)
- Dyspepsia
- Accidental Injury (study site)
- Infection (non-study site)
- Gangrene (study site)
- Spontaneous bone fracture (non-study site)
- Viral infection
- Back pain
- Angina pectoris
- Arteriosclerosis
- Cardiomegaly
- Gastrointestinal carcinoma
- Colitis
- Rhinitis
- Arthritis
- Confusion

Apligraf is contraindicated for use on clinically infected wounds.

Apligraf is contraindicated in patients with known allergies to bovine collagen.

Apligraf is contraindicated in patients with a known hypersensitivity to the components of the Apligraf agarose shipping medium listed below:

- agarose,
- L-glutamine,
- hydrocortisone,
- human recombinant insulin,
- ethanolamine,
- O-phosphorylethanolamine,
- adenine,
- selenious acid,
- DMEM powder,
- HAM's F-12 powder,
- sodium bicarbonate,
- calcium chloride

Standard of Care (SOC) Treatment

SOC consists of: 1) moist wound dressings, 2) debridement of necrotic/non-viable tissue, 3) infection surveillance and management and 4) offloading of weight bearing from vicinity of the ulcer.

In this study, the moist wound dressings include normal saline gel which is then covered with a non-adhesive foam and secured with conforming roller gauze and dressed with Coban.

The risks of SOC procedures are as follows:

Use of Wrap and Bandages

Tightness - Some subjects may experience a sense of tightness after the study doctor or staff apply the bandages over the treatment area.

Contact Dermatitis - Some subjects may experience a localized skin reaction to the bandages

Use of the offloading boot

Imbalance – Some subjects may have initial or long-term difficulty walking with the offloading boot.

Restriction of activities/movement – Some subjects may experience an inability or reduction in ability to do things that they were once able to do (i.e., wear shoes on the foot, ambulate, etc.)

Debridement Procedure

The risks associated with the debridement procedure are as follows:

- Pain - Most patients will experience pain either during or after the debridement procedure.
- Bleeding – Most patients will experience bleeding of the ulcer after debridement
- Infection - Few patients will develop an infection after debridement

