8.1.2 SCREENING VISIT 2 (-1 WEEKS [7 DAYS] ± 3 DAYS)

1. Review Eligibility Criteria (Inclusion/Exclusion)
2. Review Study Compliance with the Subject (Treatment Compliance Review)
3. Perform Sharp Debridement on Study Ulcer, if needed (Debridement)
4. Collect Images of the DFU (Photography)
5. Perform Ulcer Assessments
6. Treat Subject Using SOC Procedures (Standard of Care)
7. Apply Boot, if applicable (Boot Application)
8. Document Adverse Events
9. Document Concomitant Medications & Procedures (ConMeds and Other Procedures)

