- **MRU Assessment (Weeks 1 – 12, Follow-Up Weeks 1 & 2)**

As applicable, the site will document the following for the subject's previous visit week:

- Any and all DRG Codes, using ICD-10, that were or would be applied to the subject
- The associated CPT codes and modifiers for those CPT codes

- **Concomitant Medications (All Study Visits)**

Sites will query the subjects at each visit about any medications they are currently taking. Only medications that (1) affect the wound area, (2) affect the limb, (3) are related to the treatment of the wound, (4) are being used to treat any AEs that develop during this study, will be documented. The name, indication/reason for use, dose, route, frequency, start/stop date, and whether the medication is being used to treat any adverse events will be noted.

- **Assessment of Adverse Events (All Study Visits after Screening Visit 1)**

After the initial screening visit, sites will report full information on those AEs possibly, probably, or definitely-related to the investigational product or study procedure. Other AEs that are not related or unlikely related will only have basic information collected (Stop and Start Date). If these AEs change in relationship (e.g., an ongoing unrelated AE becomes possibly related) full information will be collected.

Sites will collect the AE onset date and a description of the event. The sites will then make a determination as to whether the AE is Serious or not and will grade its severity marking it as either (1) mild, (2) moderate, or (3) severe. For any treatment or procedure-related SAEs that are graded as (1) possibly, (2) probably or (3) definitely-related, the site will also indicate whether the event is anticipated or unanticipated. Definitions of these terms can be found in the following section of the protocol.

Sites will also note the action taken (none, medication given, hospitalization required, surgical intervention, or other), and the outcome of the AE (resolved with or without sequelae, death, ongoing, or other). If available, an adverse event resolution date will be noted. The site will also make a determination as to whether the AE caused the subject to discontinue participation in the study.

See Section 8.3 below for more information on AE definitions and procedures.

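### By-arm tables of 'all' adverse events and SAEs have no onset window, so events from the pre-randomization SOC phase are counted under the arm assigned later

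*SAP*

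**What the plan says.** **When events are collected.** Protocol 8.3.7: "The study Investigator will record all reportable events with start dates occurring any time after informed consent is obtained". Protocol 8.2 heads its instruction "Assessment of Adverse Events (All Study Visits after Screening Visit 1", and the Screening Visit 2 checklist (8.1.2) includes "Document Adverse Events". The adverse-event row of Table 2 is also marked at that visit.

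**What subjects receive then.** The synopsis (Subject Duration) puts every subject on SOC for up to two weeks, give or take three days, before Day 0. Sharp debridement is done as needed. Protocol 8.3.3 makes SOC application and sharp debridement the study procedure, so a screening event can qualify as procedure-related.

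**What is compared.** SAP 10.7: "Treatment Emergent AE's (TEAE) are defined as events with an onset on or after the first randomized treatment". Later in the same section: "Treatment groups will be compared with respect to the incidence of adverse events (all and TEAEs". The next sentence of 10.7 adds breakdowns by body system, preferred term, severity and relationship, without limiting them to TEAEs. Protocol 9.4.7 plans by-arm summaries of all AEs and of SAEs and does not use the treatment-emergent concept. The synopsis safety endpoint is "Incidence of all investigational product, procedure, and/or wound-related adverse events or serious adverse events", with no start date. The safety population (SAP 8.3) restricts which subjects are analysed, not which event dates.

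**The concern.** An event that precedes randomization cannot have been caused by the allocated treatment. If it is counted under the arm the subject later joins, it raises the incidence in every arm, moves the risk ratio towards 1 and adds noise, with only 38 subjects per arm. It also attributes an event to a treatment that had not begun.

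The route is real because of how events are defined. Under Protocol 8.3.1, product- or procedure-related events count as adverse events at any time, while events regardless of relationship are added only after first randomized treatment. Screening events that reach the database with full detail will therefore mostly be procedure-related ones. The protocol leads one to expect some: its debridement risks (2.3.1) include "Pain - Most patients will experience pain either during or after the debridement procedure".

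**Working it through.** **1. Which outputs are exposed**

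| Output | Onset window | Screening events enter? |
|---|---|---|
| SAP 10.7, TEAE comparison and TEAE summaries by severity and relationship | From first randomized treatment | No |
| SAP 10.7, 'all' comparison and its breakdowns | None | Yes |
| SAP 10.7, SAE summary | None stated | Yes |
| Protocol 9.4.7, all AEs and SAEs | None | Yes |
| Protocol 9.4.7, device-related AEs | None | No: no product is applied before Day 0 |
| Safety endpoint (synopsis, Table 3) | None | Procedure- and wound-related events, yes |
| SAP 11.1.3, Fisher's exact test | None | Device-related, no; specific complications, unclear |

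**2. Effect on subject-level incidence**

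The documents give no adverse-event rate for this trial, so there is no planned figure to reproduce. All rates below are assumptions. Let s be the proportion of subjects with a screening event, equal across arms, and p the post-randomization incidence. If the two are independent:

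- 'all AE' incidence = 1 − (1 − s)(1 − p)
- 'all AE' risk difference = (1 − s)(p1 − p2)

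For p = 20% v 40%:

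| s | 'All' incidence | Risk difference | Risk ratio |
|---|---|---|---|
| 0 (TEAEs only) | 20% v 40% | 0.20 | 2.00 |
| 0.05 | 24% v 43% | 0.19 | 1.79 |
| 0.10 | 28% v 46% | 0.18 | 1.64 |
| 0.20 | 36% v 52% | 0.16 | 1.44 |
| 0.30 | 44% v 58% | 0.14 | 1.32 |

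At s = 0.10, the ratio for 10% v 30% falls from 3.0 to 1.95, and for 30% v 50% from 1.67 to 1.49.

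**3. A plausible s**

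Suppose screening events occur at the SOC arm's constant hazard. Then s = 1 − (1 − p_SOC)^(screening weeks / weeks on study). Screening is 2 weeks. Time on study is taken as 14 weeks (12 of treatment plus 2 of confirmation) or, as an assumed short case after early closure, 6 weeks.

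| SOC incidence (assumed) | s, 14 weeks | s, 6 weeks |
|---|---|---|
| 10% | 0.015 | 0.035 |
| 20% | 0.031 | 0.072 |
| 30% | 0.050 | 0.112 |

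Worked case: 1 − 0.80^(2/14) = 0.031. The risk difference shrinks by the proportion s, so by about 2% to 11%. In subjects, 38 × 0.015 = 0.6 to 38 × 0.112 = 4.3 per arm would have a screening event. A busier SOC arm gives more: incidences of 40% and 50% over 6 weeks give s = 0.157 and 0.206.

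**4. Where the model overstates the effect**

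- *Dependence.* If subjects with screening events tend also to have later ones, fewer are newly counted. In the extreme (s at most 20%, and every such subject also has a later event), 'all' stays at 20% v 40%, ratio 2.0.
- *Event counts.* Screening adds the same expected number of events to each arm. The difference in counts is unchanged in expectation; only the ratio is diluted and noise added.

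**The case against.** The strongest reply is that the undiluted contrast is already planned. The sentence that names 'all' also names TEAEs, and the bulleted severity and relationship summaries in SAP 10.7 are TEAE summaries. SAP 10.6 calls safety descriptive, and no test is named for the 'all' comparison. This stands, and it rules out the reading, which a reader might infer, that the plan hides any real safety difference.

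A reader might also infer that SOC-phase events are charged to the allograft arms in particular, or appear as product-related. The documents do not support that. Randomization spreads screening events over all three arms equally in expectation. Protocol 8.3.2 and 8.3.3 define product and procedure separately, so an event before Day 0 can properly be procedure-related only.

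The larger dilution figures are open to challenge too. The statement about debridement pain is a general risk warning, not an adverse-event rate. Debridement continues as needed through Week 11. If its pain were routinely recorded, post-randomization incidence would also be high, and 20% v 40% would not fit.

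Finally, 'all' is never defined, so inclusion of screening events is the natural reading rather than an explicit statement.

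What survives is that the 'all' comparison, its severity and relationship breakdowns, the SAE summary and Protocol 9.4.7 have no window, and the protocol's own tables have no treatment-emergent counterpart. A descriptive table still places the event under an arm that did not yet exist.

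**Conclusion.** The point holds as a limited defect in the tabulation rules. Pre-randomization events, essentially procedure-related ones, would be counted by later-assigned arm in the 'all AE', procedure-related and SAE output. The effect is non-differential in expectation. It dilutes subject-level incidence comparisons and ratios; it leaves the TEAE comparison and product-related events intact.

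The size cannot be known from the documents. The shrinkage of about 2% to 11% rests on a constant SOC hazard, an assumed SOC-arm incidence of 10% to 30%, 6 or 14 weeks on study, and independence of screening and later events. Ratios as low as 1.32 require 30% of subjects to have a recorded screening event, which the documents do not establish.

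**What to change.** - **One window.** Base every by-arm AE and SAE table and comparison, and the safety endpoint, on events with onset or worsening from first randomized treatment up to study exit.
- **Screening events.** List events between consent and first treatment separately, without arm columns.
- **One TEAE definition in SAP 10.7.** Merely deleting 'all' from the comparison sentence is unsafe. Section 10.7 holds a second definition tied to an active phase bounded by the first and last dose of test article. Read literally, it could drop events in the confirmation weeks, and it does not fit SOC-alone subjects, who may have no test article. Replace it with the single window above.
- **Alignment.** Bring Protocol 9.4.7 and SAP 11.1.3 into line, and reconcile Protocol 8.2, 8.3.1 and 8.3.7 on when collection starts and which events it covers.

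The cost is a few wording changes and a filter on onset dates, which Protocol 8.2 already has sites collect. The all-AE by-arm table is dropped, but its events remain listed. One limit remains: Protocol 8.1.3 puts Day 0 debridement before randomization, and a filter by date alone cannot separate those events from later ones that day. The SAP should say how they are counted.
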